9. ADVERSE EVENT RECORDING AND REPORTING

9.1 Recording Requirements

- Research subjects will be routinely questioned about treatment related adverse events at each study visit. All possible, if any, non-serious examples are pain, erythema/redness, skin thinning/atrophy, infection, color/texture change, swelling, telangiectasia, graft shrinkage/rejection and need for additional surgery. Serious adverse events are not expected to be seen at any moment of the study since medication has been shown to be safe to the patient. In addition, patients will be evaluated for early post-operative complications (within 2 weeks of surgery) not related to study drug treatment. Example of that are wound dehiscence, graft necrosis, infection, bleeding, partial/complete graft failure and/or ectropion. Events will be followed until it resolves or stabilizes; if needed other treatment (eg. antibiotics) will be added to manage adverse event.

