### 10.2 Secondary endpoints or outcome measure(s)

- The secondary endpoints that will be measured during the clinical study are patient and surgeon satisfaction using the scar assessment scale (POSAS) developed and previously published by Draaijers et al., treatment related adverse events, and early post-operative complications.

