### 10.4 Analysis Population (if applicable)

- Independent sample t-test will be applied to the primary outcome analysis (i.e., comparison of mean changes in graft size from pre-treatment to the last follow up). In addition, for the secondary outcome we will utilize repeatedly measured POSAS scores over time by using longitudinal linear mixed effects model which can further determine the time dependency of the treatment effect. The model will include treatment group (group 0 for placebo and 1 for treatment), time (0=two-three weeks post-op visit / first injection, 1=second injection, 2=third injection, 3=fourth injection, 4=two to three weeks after last injection), and group x time. Both effects (1. group difference in the pre-treatment measurement 2. time trend of the control) will be considered fixed effects and the individual 2-3 weeks post-operative measurement random. Group x time effect is expected to be an increased slope of the treatment group over time. For the other outcome measurements, we will apply the same methods. Also statistical methods will include intention to treat (ITT) analysis to compare all subjects in the groups randomly assigned. We will exclude anyone who gets partial treatment, exit early or is lost to follow up; in those cases we will replace patient with another subject that meets the criteria. Discussed with [name] at MGH biostatistics.

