#### **10.5 Effectiveness Analysis (if applicable)**

- As described above, the population analysis that will be employed in the primary and secondary endpoints is a sample t-test with a level of significance of 0.050.

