#### **10.6 Safety Analysis**

- The safety analysis of the study drug is our secondary endpoint that will be analyze with a sample t-test using a level of significance of 0.050.

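### Adverse events and early complications are to be compared with a t-test, which does not suit yes/no outcomes and gives no result when no patient has the event

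*SAP*

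**What the plan says.** SAP section 10.6 describes the safety analysis as a secondary endpoint "that will be analyze with a sample t-test using a level of significance of 0.050". Section 10.5 says that "the population analysis that will be employed in the primary and secondary endpoints is a sample t-test with a level of significance of 0.050". Section 10.4 gives an independent-samples t-test for graft size and a linear mixed model for POSAS scores, then adds: "For the other outcome measurements, we will apply the same methods".

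Section 10.2 includes among the secondary endpoints "treatment related adverse events, and early post-operative complications". Protocol section 9.1 lists the adverse events as "pain, erythema/redness, skin thinning/atrophy, infection, color/texture change, swelling, telangiectasia, graft shrinkage/rejection and need for additional surgery" and the early complications as "wound dehiscence, graft necrosis, infection, bleeding, partial/complete graft failure and/or ectropion". No severity score, event count or other per-patient measure is defined for them. Neither document names an exact test, a chi-square test, a risk difference or an interval for proportions.

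Protocol section 9.1 expects no serious adverse events, and section 1.2 cites a retrospective series of 19 patients reported as free of complications. SAP section 10.3 plans up to 15 patients per arm and allows analysis once 10 per arm have completed.

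**The concern.** A t-test takes its standard error from the spread seen in the data. On a yes/no outcome that nobody has, the spread is zero and the test does not exist. The documents' own background makes empty rows in the safety table plausible, at least for the more serious events.

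In a trial this small, the useful safety statement about an event that was not seen is how large a risk the data still allow. The stated method cannot supply it. The mixed model in section 10.4 does not help, because it is also a linear model for a continuous outcome.

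**Working it through.** **Inputs.** From SAP section 10.3: 10 per arm at the earliest analysis and 15 per arm at full enrolment, with 12 as the stated dropout-adjusted number. From SAP sections 10.3 to 10.6: a two-sample t-test at 0.05, taken as the equal-variance form in 10.3. Event rates are assumptions (2%, 5% and 10%, the same in both arms), because the documents give none.

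**The plan's own figure.** There is none for safety. The one sample-size figure concerns graft size: a difference of 13.2 with a standard deviation of 10 and 10 per arm gives 79.7% power by the noncentral t, which agrees with the stated 80%. The 10 per arm was therefore not chosen with event rates in mind.

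**The t-test on yes/no data.** With x and y events among n patients per arm, a = x/n and b = y/n:

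- pooled variance v = [n·a(1−a) + n·b(1−b)] / (2n−2)
- t = (a − b) / √(2v/n)

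If x = y = 0, then v = 0 and t = 0/0. The unequal-variance form fails in the same way, since both variances are zero.

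**How often no patient has the event.** For one event type with common rate p, the chance is (1−p)^(2n):

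| Assumed rate | 10 per arm | 15 per arm |
|---|---|---|
| 2% | 0.98^20 = 67% | 0.98^30 = 55% |
| 5% | 0.95^20 = 36% | 0.95^30 = 21% |
| 10% | 0.90^20 = 12% | 0.90^30 = 4% |

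These chances apply to each event type separately, and Protocol section 9.1 lists many.

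**What is lost.** The exact two-sided 95% upper limit for 0/n is 1 − 0.025^(1/n), which is 30.8% for 0/10 and 21.8% for 0/15. For the risk difference at 0 v 0, the Newcombe 95% interval is ± z²/(n + z²) with z² = 3.84. This is ±27.8 percentage points at 10 per arm and ±20.4 at 15. Over assumed rates of 1–30% v 1–10% its coverage was at least 95.2%.

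**What the t-test does when events occur.** Full enumeration of two binomials gives these type I error rates for the nominal 5% test:

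| Common rate | 10 per arm | 12 per arm | 15 per arm |
|---|---|---|---|
| 5% | 0.1% | 0.2% | 0.5% |
| 10% | 0.9% | 1.5% | 2.5% |
| Maximum over all rates | 4.2% | 6.4% | 5.5% |

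Example, 4/10 v 0/10: v = 2.4/18 = 0.133, standard error √(2 × 0.133/10) = 0.163, t = 0.4/0.163 = 2.45, p = 0.025. Boschloo's exact test gives 0.042 and Fisher's 0.087. For 4/15 v 0/15 the three p-values are 0.032, 0.043 and 0.100.

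**The case against.** Much of the case on the other side stands.

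- **False positives.** A reader might infer that the t-test would produce false safety signals. It does not: it is conservative for rare events, and its worst case is 6.4%.
- **Wrong conclusions from p-values.** In the 4 v 0 tables the t-test p-value is well below Fisher's, but Boschloo's test is also below 0.05. The gap does not show that a conclusion would change.
- **Interval coverage.** If trials with no events count as misses, a 95% t-interval covers a true 10% v 0% difference in only 65% (10 per arm) or 79% (15 per arm) of trials. That is the no-event case counted again: 1 − 0.9^10 = 65% and 1 − 0.9^15 = 79%. When the interval exists in that setting, its coverage is above 99%, so these figures do not show that the standard error is too small with few events. The SAP also promises no safety interval.
- **Most likely result.** At 5%, exactly one event among 20 patients (20 × 0.05 × 0.95^19 = 37.7%) is slightly likelier than none (35.8%). Only serious events are called unexpected; pain, redness and swelling have no stated rate and may be common.
- **Little lost at 0 v 0.** Fisher's test gives p = 1 there, which is no more informative. The gain comes from limits and intervals, not from another p-value.
- **Early complications.** Protocol section 9.1 places these within two weeks of surgery and calls them unrelated to the study drug, and section 7.2 starts injections 2–3 weeks after surgery. The arm comparison is essentially a pre-treatment one, so the point bears mainly on treatment-related adverse events.
- **Undefined variable.** The SAP never defines the safety variable, so a per-patient count is possible. A t-test on counts is also 0/0 when all counts are zero.

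None of this supplies a method for proportions or a result for an event that nobody has.

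**Conclusion.** The plan is wrong as written. It assigns a t-test to outcomes listed as present or absent, and that test has no value when neither arm has the event. The chance of this per event type ranges from 4% (10% rate, 15 per arm) to 67% (2% rate, 10 per arm), and these rates are assumptions. In those cases the plan cannot state that a risk of up to about 31% (0/10) or 22% (0/15) in an arm remains compatible with the data.

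The documents do not support a claim that the method inflates false positives or misstates the uncertainty in both directions. The importance is minor to moderate: a secondary endpoint is affected, while the primary conclusion and the sample size are not.

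**What to change.** In SAP section 10.6, replace the t-test. For each event type, report by arm:

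- the number and percentage of patients with at least one event;
- exact 95% limits for each arm;
- the risk difference with a Newcombe 95% score interval.

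If a p-value is wanted, name a single exact test before unmasking, for example Boschloo's. Leaving a choice between Boschloo and Fisher would let the analyst pick the verdict in a table such as 4/10 v 0/10 (0.042 v 0.087). Fisher's test is also conservative at this size.

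In sections 10.4 and 10.5, limit the t-test and the carry-over of methods to graft size and POSAS scores.

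The cost is SAP wording only. The exact p-value will be somewhat larger than the t-test's in some tables, such as 0.042 instead of 0.025 for 4/10 v 0/10.

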#### **10.7 Interim Analysis**

- No interim analysis is planned.
